APPENDIX 2. ECG AND VITAL SIGN ABNORMALITIES

Important abnormalities from the ECG readings are summarized below:

Abnormality	ECG Parameter			
	HR	PR	QRS	QTcF
Abnormalities on actual values				
Abnormally low	<45 bpm	NA	-	-
Abnormally high	≥120 bpm	>220 msec	≥120 msec	-
Borderline prolonged QT (males)	-	-	-	450 msec to ≤480 msec
Borderline prolonged QT (females)				470 msec to ≤480 msec
Prolonged QT	-	-	-	481 msec to ≤500 msec
Pathologically prolonged QT	-	-	-	>500 msec
Abnormalities on changes from baseline				
Normal QTcF change	-	-	-	<30 msec
Borderline QTcF change	-	-	-	30 msec to ≤60 msec
Abnormally high QTcF change	-	-	-	>60 msec

Abbreviations: bpm = beats per minute; HR = heart rate; NA = not applicable; PR = PR interval; QRS = QRS interval; QTcF = QT interval corrected for heart rate using Fridericia's formula.

Important abnormalities for vital signs are summarized below:

Abnormality	Vital Signs Parameter		
	HR	DBP	SBP
Abnormally low	≤45 bpm	≤50 mmHg	≤90 mmHg
Grade 1 or mild	-	>90 mmHg to <100 mmHg	>140 mmHg to <160 mmHg
Grade 2 or moderate	-	≥100 mmHg to <110 mmHg	≥160 mmHg to <180 mmHg
Grade 3 or severe	-	≥110 mmHg	≥180 mmHg
Abnormally high	≥120 bpm	-	-

Abbreviations: DBP = diastolic blood pressure; HR = heart rate; SBP = systolic blood pressure.

	Grade 1	Grade 2	Grade 3	Grade 4
Fever ^a	38.0 to <38.6°C (100.4 to <101.5°F)	≥38.6 to <39.3°C (≥101.5 to <102.7°F)	≥39.3 to <40.0°C (≥102.7 to <104.0°F)	≥40.0°C (≥104.0°F)

a. Non-axillary temperatures only.

For tachypnea and hypoxia, refer to the grading scale in [Table 9](#).

APPENDIX 3. DIAGNOSTIC CRITERIA AND MANAGEMENT FOR ANAPHYLAXIS

Diagnostic Criteria for Anaphylaxis

Anaphylaxis is highly likely when any one of the following 3 criteria are fulfilled:

1. Acute onset of an illness (minutes to several hours) with involvement of the skin, mucosal tissue, or both (e.g., generalized hives, pruritus or flushing, swollen lips, -tongue, -uvula)
and **at least one** of the following:
 - a. Respiratory compromise (e.g., dyspnea, wheeze-bronchospasm, stridor, reduced peak expiratory flow, hypoxemia)
 - b. Reduced blood pressure or associated symptoms of end-organ dysfunction (e.g., hypotonia [collapse], syncope, incontinence)
2. Two or more of the following that occur rapidly after exposure to a likely allergen for that subject (minutes to several hours):
 - a. Involvement of the skin-mucosal tissue (e.g., generalized hives, itch-flush, swollen lips-tongue-uvula)
 - b. Respiratory compromise (e.g., dyspnea, wheeze-bronchospasm, stridor, reduced peak expiratory flow, hypoxemia)
 - c. Reduced blood pressure or associated symptoms (e.g., hypotonia [collapse], syncope, incontinence)
 - d. Persistent gastrointestinal symptoms (e.g., crampy abdominal pain, vomiting)
3. Reduced blood pressure after exposure to known allergen for that subject (minutes to several hours):
 - a. Systolic blood pressure <90 mmHg or >30% decrease from that person's baseline

Management of Anaphylaxis

1. **Epinephrine:** When a subject meets any of the diagnostic criteria, the subject should receive epinephrine immediately, as it is the treatment of choice in anaphylaxis. Aqueous epinephrine, 0.01 mg/kg (maximum dose, 0.5 mg) administered intramuscularly every 5 to 15 minutes as necessary, is the recommended dosage for controlling symptoms and maintaining blood pressure. The 5-minute interval between injections can be liberalized to permit more frequent injections if deemed necessary by the clinician.
2. **Oxygen and adrenergic agonists:** High-flow oxygen (through a nonrebreather mask or endotracheal tube) should be administered to subjects experiencing respiratory symptoms or hypoxemia. Those who are hemodynamically unstable might benefit from oxygen as well. Inhaled β_2 -agonists, such as albuterol, might be useful for bronchospasm refractory to epinephrine.

3. **Positioning of the subject:** Subjects in anaphylactic shock (i.e., those with anaphylaxis and signs of critical organ hypoperfusion) should be placed in a recumbent position with the lower extremities elevated unless precluded by shortness of breath or vomiting.
4. **Fluid resuscitation:** Subjects who remain hypotensive despite epinephrine should have aggressive fluid resuscitation. Large volumes of crystalloid might be needed in the first 5 to 10 minutes; in severe reactions with hypotension, up to 35% of the blood volume might extravasate in the first 10 minutes, and vasodilatation can cause pooling, with even more reduction in the effective blood volume and thus distributive shock.
5. **Vasopressors:** Potent vasopressors, such as noradrenaline, vasopressin, or metaraminol, might be required to overcome vasodilatation if epinephrine and fluid resuscitation have failed to maintain a systolic blood pressure of greater than 90 mmHg.
6. **H₁- and H₂-antihistamines:** Antihistamines (H₁- and H₂-antagonists) are slower in onset of action than epinephrine, have little effect on blood pressure, and should be considered a second-line treatment for anaphylaxis.
7. **Corticosteroids:** Because the onset of action is slow, steroids are not useful in the acute management stage. It has been suggested that their use might prevent a protracted or biphasic reaction.
8. **Glucagon for persistent hypotension in subjects taking β-blocker:** Theoretically, there are multiple mechanisms by which β-blockade could blunt the response to epinephrine. If administration of epinephrine in these subjects is ineffective, administration of glucagon can be attempted. Glucagon is thought to reverse refractory hypotension and bronchospasm by activating adenylate cyclase independent of the β-receptor; however, the occurrence and importance of this mechanism of action in anaphylaxis is unproved.
9. **Observation:** After the treatment of an anaphylactic reaction, an observation period should be considered for all subjects as the reaction might recur as the effect of epinephrine wears off (intramuscular epinephrine results in increased serum levels for an hour or more) and because of the risk of a biphasic reaction (1–72 hours after the acute reaction).

Source: [Sampson 2006](#).

APPENDIX 4. RASH MANAGEMENT

For subjects reporting rash, the following should be performed:

All rashes will be discussed between the Investigator and the Sponsor, and in case of a causal relationship between the rash and the study drug, then the following visits and assessments will be performed as indicated below and in the “Visit Schedule for Rash Management” (see [Appendix 5](#)). Unscheduled follow-up visits for close follow-up of rash will be performed based on the grade (severity) of the rash. At the Investigator’s discretion, additional visits and assessments may be performed.

The rash event should be captured in the AE section of the eCRF, as well as in more detail in the specific rash assessment pages of the eCRF.

In case of rash, blood samples need to be collected for safety laboratory testing, and processed by the local laboratory. These samples need to be collected during the unscheduled visits as described below and in [Appendix 5](#). A copy of the local laboratory reports should be anonymized and will be retrieved by the monitor.

The following parameters need to be tested: AST, ALT, creatinine, erythrocyte sedimentation rate, and a complete blood cell count (including hemoglobin, hematocrit, red blood cell [RBC] count, white blood cell [WBC] count, neutrophils, lymphocytes, monocytes, eosinophils, basophils, and platelet count).

Digital pictures need to be taken as described below and in [Appendix 5](#). Digital pictures will be anonymized and stored on the Sponsor’s secure server. Only the study team will have access to the pictures.

The subject may be treated symptomatically until the rash resolves. If the rash is considered to be most likely due to concomitant illness or non-study medication, standard management, including discontinuation of the likely causative agent, should be undertaken, and the continuation of the subject in the study should be discussed with the Sponsor.

Dermatologist fees for evaluating subjects who experience a rash will be reimbursed by the Sponsor.

The following grades are based on the DAIDS Toxicity Grading Scale ([DAIDS 2017](#)) with adaptations made by the Sponsor:

Subjects should be informed that they should contact their doctor and visit the clinic immediately (unscheduled visit, day 1 of the rash) when they notice any rash.

Grade 1 Rash

A Grade 1 rash is defined as **erythema**.

- Subjects may continue the intake of study drug(s) (at the Investigator’s discretion).
- An unscheduled visit for initial rash evaluation (day 1 of the rash) is required.
- Assessment of safety blood samples by the local laboratory is required. A copy of the local laboratory report should be anonymized and will be retrieved by the monitor.

- Digital pictures should be taken within 24 hours after the onset of the rash.
- Referral to a dermatologist is only needed if the rash diagnosis is uncertain (preferably within 24 hours after the onset of the rash). A copy of the dermatologist's report should be anonymized and will be retrieved by the monitor.
- Cetirizine, levocetirizine, topical corticosteroids, or antipruritic agents may be prescribed.
- The description of the rash should be reported per 'Unscheduled Visit in Case of Rash' in the eCRF (i.e., the initial rash assessment pages).

For close follow-up of the rash, unscheduled visits will also be performed 1 and 7 days after the initial assessment of the rash. At these visits, safety blood samples and digital pictures should be taken. The follow-up rash assessment pages of the eCRF should be completed for all follow-up visits. For these and all subsequent local laboratory blood sample assessments: a copy of the local laboratory reports should be anonymized and will be retrieved by the monitor.

If the rash is unresolved after 7 days, additional unscheduled visits may be performed at the Investigator's discretion. Upon resolution/stabilization of the rash, digital pictures should be taken and the final rash assessment pages of the eCRF should be completed.

The subject should be advised to contact the Investigator immediately if there is any worsening of the rash, if any systemic signs or symptoms appear, or if mucosal involvement develops.

In case the rash evolves from a Grade 1 to a higher grade, additional unscheduled visits have to be conducted according to the guidelines for Grade 2 or Grade 3–4 rash, respectively.

Grade 2 Rash

A Grade 2 rash is defined as **diffuse, maculopapular rash OR dry desquamation**.

- Subjects will permanently discontinue the intake of study drugs and be withdrawn from the study. No rechallenge is allowed.

Note: Subjects experiencing Grade 2 rash following the last intake of study drug may continue in the study as long as they are not re-exposed to suspect study drug.

- An unscheduled visit for initial rash evaluation (day 1 of the rash) is required.
- Assessment of safety blood samples by the local laboratory is required. A copy of the local laboratory report should be anonymized and will be retrieved by the monitor.
- Digital pictures should be taken within 24 hours after the onset of the rash.
- Referral to a dermatologist is required, preferably within 24 hours after the onset of the rash. A copy of the dermatologist's report should be anonymized and will be retrieved by the monitor.
- A biopsy is performed (preferably within 24 hours after the onset of the rash) if advised by the dermatologist. A copy of the biopsy report should be anonymized and will be retrieved by the monitor.
- Cetirizine, levocetirizine, topical corticosteroids, or antipruritic agents may be prescribed.

- The description of the rash should be reported per 'Unscheduled Visit in Case of Rash' in the eCRF (i.e., the initial rash assessment pages).

For close follow-up of the rash, unscheduled visits will also be performed 1 and 7 days after the initial assessment of the rash. At these visits, safety blood samples and digital pictures should be taken. The follow-up rash assessment pages of the eCRF should be completed for all follow-up visits. For these and all subsequent local laboratory blood sample assessments: a copy of the local laboratory reports should be anonymized and will be retrieved by the monitor.

If the rash is unresolved after 7 days:

- And there is an increase in AST/ALT of 1 or 2 times the baseline value OR an increase in AST/ALT of less than 5 times the ULN, subjects should be followed weekly with repeated local lab assessments and digital pictures until resolution of the AST/ALT abnormalities.
- And there is no increase in AST/ALT, additional unscheduled visits (including local lab assessments and digital pictures) may be performed at the Investigator's discretion.

Upon resolution/stabilization of the rash, digital pictures should be taken and the final rash assessment pages of the eCRF should be completed.

The subject should be advised to contact the Investigator immediately if the rash fails to resolve (after more than 2 weeks), if there is any worsening of the rash, if any systemic signs or allergic symptoms develop, or if mucosal involvement develops.

In case the rash evolves from a Grade 2 to a Grade 3–4 rash, additional unscheduled visits must be conducted according to the guidelines for Grade 3–4 rash.

Grade 3 or Grade 4 Rash

A Grade 3 rash is defined as:

- **vesiculation, moist desquamation, or ulceration** OR
- **cutaneous event with one of the following** (revised by the Sponsor):
 - elevations in AST/ALT more than 2× baseline value and $\geq 5 \times$ ULN
 - fever $>38^{\circ}\text{C}$ or 100°F
 - eosinophils $>1000/\text{mm}^3$
 - serum sickness-like reaction

A Grade 4 rash is defined as:

- **exfoliative dermatitis** OR
- **a generalized rash with mucous membrane involvement** OR
- **erythema multiforme** OR
- **Stevens-Johnson Syndrome** OR
- **rash associated with necrosis requiring surgery**

- Subjects will **permanently discontinue** the intake of all study drug(s) and be withdrawn from the study with Grade 3 or 4 rash identified. No rechallenge is allowed.
- An unscheduled visit for initial rash evaluation (day 1 of the rash) is required.
- Assessment of safety blood samples by the local laboratory is required on the day of initial rash evaluation and the day thereafter (days 1 and 2 of the rash), and as indicated below. A copy of the local laboratory report should be anonymized and will be retrieved by the monitor.
- Digital pictures should be taken within 24 hours after the onset of the rash and on day 1 of the rash, and as indicated below.
- Referral to a dermatologist is required, preferably within 24 hours after the onset of the rash. A copy of the dermatologist's report should be anonymized and will be retrieved by the monitor.
- A biopsy should be performed within 24 hours after the onset of the rash. A copy of the biopsy report should be anonymized and will be retrieved by the monitor.
- Appropriate management should be undertaken and subjects should be followed until resolution of the rash.
- The description of the rash should be reported per 'Unscheduled Visit in Case of Rash' in the eCRF (i.e., the initial rash assessment pages). The follow-up rash assessment pages of the eCRF should be completed for all follow-up visits.

For close follow-up of the rash, unscheduled visits will be performed as follows:

- Follow-up visits on days 2, 3, and 4 of the rash are required. Additional safety blood samples and digital pictures are to be taken on these days only if the subject's AST/ALT on day 1 and/or day 2 of rash $>2\times$ baseline value, and/or $\geq 5 \times$ ULN and/or in case of rash progression. For these and all subsequent local laboratory blood sample assessments: a copy of the local laboratory report should be anonymized and will be retrieved by the monitor.
- A follow-up visit on day 6 of the rash is required and additional safety blood samples and digital pictures are to be taken regardless of the day 1/2 AST/ALT levels or rash progression.
- Thereafter, weekly follow-up visits are required (or more frequently at the Investigator's discretion) as long as Grade 3–4 rash is present. Once Grade 3–4 rash has resolved to Grade ≤ 2 , follow-up should be performed according to the instructions for follow-up visits for Grade 1 or Grade 2 rash, respectively.
- As long as the rash remains Grade 3 or 4, additional safety blood samples and digital pictures are required at these weekly follow-up visits only if the subject's AST/ALT on day 6 of rash is still $>2\times$ baseline value and/or $\geq 5 \times$ ULN and/or in case of rash progression, until resolution or stabilization of the AST/ALT elevations.

Upon resolution/stabilization of the rash, digital pictures should be taken and the final rash assessment pages of the eCRF should be completed.

Subjects should be advised to contact the Investigator immediately if they notice any worsening of the rash.

A complete summary of the guidelines for rash management is given in [Appendix 5](#).

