7.2. Subject Exclusion Criteria

Subjects must NOT meet any of the following exclusion criteria:

1. History of any hypersensitivity or allergic reaction to zanamivir or other neuraminidase inhibitors (i.e., laninamivir, oseltamivir, peramivir), or to excipients of the CD388 Injection drug formulation; or history of drug-induced exfoliative skin disorders (e.g., Stevens-Johnson syndrome [SJS], erythema multiforme, or toxic epidermal necrolysis [TEN]).
2. History of any of the following:
 - a. Allergies, anaphylaxis, skin rashes (foods such as milk, eggs, medications, vaccines, polyethylene glycol [PEG], etc.).
 - b. Chronic immune-mediated disease, positive first-degree family history of autoimmune diseases.
 - c. Atopic dermatitis or psoriasis.
 - d. Bleeding disorder.
 - e. Psychiatric condition, seizures, hallucinations, anxiety, depression, or treatment for mental conditions.
 - f. Migraines.
 - g. Syncope, or vasovagal syndrome with injections or blood draws.
 - h. Cardiac arrhythmia.
3. Subjects with one or more of the following laboratory abnormalities at screening as defined by the DAIDS Table for Grading the Severity of Adult and Pediatric Adverse Events v2.1 ([DAIDS 2017](#)):
 - a. Serum creatinine, Grade ≥ 1 ($\geq 1.1 \times$ upper limit of normal [ULN])
 - b. Pancreatic amylase or lipase, Grade ≥ 2 ($\geq 1.5 \times$ ULN)
 - c. Aspartate aminotransferase (AST) or alanine aminotransferase (ALT), Grade ≥ 1 ($\geq 1.25 \times$ ULN)
 - d. Total bilirubin, Grade ≥ 1 ($\geq 1.1 \times$ ULN)
 - e. Any other toxicity Grade ≥ 2 , except for Grade 2 elevations of triglycerides, low density lipoprotein cholesterol, and/or total cholesterol.
 - f. Any other laboratory abnormality considered to be clinically significant by the Investigator.

Note: Retesting of abnormal laboratory values that may lead to exclusion will be allowed once without prior asking approval from the Sponsor. Retesting will take place during a scheduled or unscheduled visit during screening. Subjects with a normal value at retest may be included.

4. Alcohol or drug addiction in the past 2 years.
5. Experiencing symptoms of acute illness or chronic disease within 14 days prior to check-in to the CRU.
6. At screening, a positive result for hepatitis B virus surface antigen, hepatitis C virus antibody, or human immunodeficiency virus (HIV) antibody.

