7.4. Subject Withdrawal Criteria

7.4.1. Subject Stopping Rules

Subjects in Cohorts 2A, 2B, 3A, and 3B will be followed through Outpatient Visit 4 (OV4) of the first dosing period, and will not receive the second single dose:

- If the subject develops anaphylaxis or a related Grade 3 or Grade 4 AE
- If the subject has a persistent (i.e., >5 days with no response to treatment) Grade ≥ 2 rash considered related to the investigational drug by the Principal Investigator ([Appendix 4](#))
- If the Investigator believes that it is in the best interest of the subject to not receive a second dose
- If the subject no longer meets all eligibility criteria prior to the second single dose
- If the subject becomes pregnant prior to the second single dose

If a subject is removed from the study for any reason, the subject will be followed for resolution of any ongoing AE(s).

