APPENDIX 5. VISIT SCHEDULE FOR RASH MANAGEMENT FOR ADULT SUBJECTS

This visit schedule summarizes the visits and assessments to be performed in case of rash. At the Investigator's discretion, additional visits and assessments may be performed. For all rashes, please also complete the specific rash assessment pages of the eCRF for all visits. Local laboratory blood sample assessments will be documented/collected as described in the text above.

Rash Day	Grade 1 Rash	Grade 2 Rash	Grade 3 or 4 Rash
Rash day 1 ^a	
 Study drug(s) MAY be CONTINUED. Unscheduled visit for initial rash evaluation REQUIRED. Assessment of safety blood sample by local laboratory REQUIRED. Digital pictures REQUIRED (within 24 h). Referral to dermatologist ONLY IF rash diagnosis uncertain (within 24 h). 	
 Study drug(s) MUST be permanently DISCONTINUED if the subject has a persistent (i.e., >5 days with no response to treatment) Grade ≥ 2 ^b rash considered related to CD388 by the Investigator. Rechallenge is NOT ALLOWED. Unscheduled visit for initial rash evaluation REQUIRED. Assessment of safety blood sample by local laboratory REQUIRED. Digital pictures REQUIRED (within 24 h). Referral to dermatologist REQUIRED (within 24 h). Biopsy IF ADVISED by dermatologist (within 24 h). 	
 Study drug(s) MUST be permanently DISCONTINUED. Rechallenge is NOT ALLOWED. Unscheduled visit for initial rash evaluation REQUIRED. Assessment of safety blood sample by local laboratory REQUIRED. Digital pictures REQUIRED (within 24 h). Referral to dermatologist REQUIRED (within 24 h). Biopsy REQUIRED (within 24 h).
Rash day 2	
 Follow-up visit REQUIRED. Assessment of safety blood sample by local laboratory REQUIRED. Digital pictures REQUIRED. 	
 Follow-up visit REQUIRED. Assessment of safety blood sample by local laboratory REQUIRED. Digital pictures REQUIRED. 	
 Follow-up visit REQUIRED. Assessment of safety blood sample by local laboratory REQUIRED. Digital pictures REQUIRED.

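### The protocol's rash rules conflict: on withdrawal after a related Grade 3/4 rash, on the fever limit that makes a rash Grade 3, and on dose 2 after a brief related Grade 2 rash

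*Protocol*

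**What the plan says.** Four places in the protocol govern a drug-related rash: the synopsis (Subject Stopping Rules), Section 7.4.1, Appendix 4 and Appendix 5. Only Cohorts 2A, 2B, 3A and 3B are due a second dose.

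- **Appendix 4**, whose grade-specific steps apply once a rash is judged causally related, states for Grade 2: "Subjects will permanently discontinue the intake of study drugs and be withdrawn from the study. No rechallenge is allowed". It sets no condition on duration or treatment response. A note lets a subject whose Grade 2 rash follows the final administration stay in the study, provided there is no re-exposure. For Grade 3 and 4 it also requires permanent discontinuation, withdrawal and no rechallenge, without any such note.
- **Section 7.4.1 and the synopsis** list reasons to withhold dose 2 while keeping the subject in follow-up to OV4 of the first period. One is a related Grade 3 or 4 AE. The rash item, which itself cites Appendix 4, opens "If the subject has a persistent (i.e., >5 days with no response to treatment" and concerns related rash of Grade 2 or higher. Two further items are "If the Investigator believes that it is in the best interest of the subject to not receive a second dose" and "If the subject no longer meets all eligibility criteria prior to the second single dose".
- **Appendix 5**, Grade 2 column, says that study drug "MUST be permanently DISCONTINUED if the subject has a persistent (i.e., >5 days with no response to treatment", and then, as a separate sentence, "Rechallenge is NOT ALLOWED".
- **Fever.** Appendix 4 makes any cutaneous event Grade 3 if it comes with fever, giving the limit as above 38°C or 100°F. The fever table in Appendix 2 starts at 38.0°C and equates that with 100.4°F.

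**The concern.** In a first-in-human trial, the rules for a drug-related rash should give one answer on re-exposure, one on follow-up, and one number for any limit that decides either. These texts do not.

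The follow-up conflict matters most. A subject with a severe related rash is one whose later PK, anti-drug antibody and safety data are most informative. Withdrawal removes the scheduled visits that would supply them. Appendix 4 continues its own rash visits, but their listed tests are local safety laboratory tests (transaminases, creatinine, sedimentation rate, blood count), not PK or ADA.

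**Working it through.** No figure in the plan needs reproducing. The check sets the texts side by side and then counts what withdrawal would lose.

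**Outcome by case, after dose 1 in Cohorts 2A to 3B**

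| Related rash | Appendix 4 | 7.4.1 and synopsis | Appendix 5 |
|---|---|---|---|
| Grade 2, transient or responding | No dose 2 | Rash criterion not met | Discontinuation not triggered; rechallenge sentence carries no condition |
| Grade 2, persistent | No dose 2 | No dose 2 | No dose 2 |
| Grade 3 or 4 | No dose 2; withdrawn | No dose 2; followed to OV4 | No dose 2 |

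The sources disagree on re-dosing only in the first row. In the third row they agree on dosing and differ only on whether the subject stays in the study. For Grade 2 the withdrawal conflict is weaker, because once dose 2 is refused, dose 1 can be read as the final administration and the Appendix 4 note then allows the subject to continue.

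**Subjects due dose 2** (Section 6.1 and Table 5). 4 cohorts × (2 + 9) = 44, made up of CD388 4 × (1 + 7) = 32 and placebo 4 × (1 + 2) = 12.

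**Scheduled samples lost per withdrawn subject** (Table 1; the rash day is assumed). An early discontinuation calls for one set of OV4 procedures.

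- Withdrawn after the Day 7 sample, PK: Days 9, 11, 14, 21, 30 plus OV1 to OV4 = 5 + 4 = 9 remaining, against 1, so 8 fewer.
- Withdrawn after the Day 7 sample, ADA: Days 14 and 30 plus OV1 to OV4 = 2 + 4 = 6, against 1, so 5 fewer.
- Withdrawn after Day 30: OV1 to OV4 = 4 of each, against 1, so 3 fewer of each.
- Each loss is one smaller if OV2 is omitted, as Table 1 permits.

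**Fever limit.** (100 − 32) × 5/9 = 37.8°C, and 38.0 × 9/5 + 32 = 100.4°F. The two limits in the Grade 3 criterion disagree between 37.8 and 38.0°C. As Appendix 4 stands, Grade 2 already ends dosing, so the effect on re-dosing is confined to Grade 1 erythema in that band. There Appendix 4 otherwise leaves continued dosing to the Investigator's discretion; the lower limit would turn this into mandatory discontinuation and withdrawal.

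**The case against.** The strongest reply concerns re-dosing. Section 7.4.1 lists reasons to withhold dose 2; it never says that a subject outside the list must receive it. Appendix 4 adds a stricter condition, and the rash item refers the site to Appendix 4. Other gates exist too. Eligibility is reconfirmed before dose 2, and exclusion 2a covers a history of "Allergies, anaphylaxis, skin rashes (foods such as milk, eggs, medications, vaccines, polyethylene glycol [PEG], etc"; a rash attributed to CD388 could plausibly meet it. Dose 2 also depends on acceptable cumulative first-dose safety (Section 6.1) and on Investigator judgement, and Appendix 4 requires that "All rashes will be discussed between the Investigator and the Sponsor". All of this stands. A reader might infer that the protocol orders a second dose after a brief related Grade 2 rash, or that no site could comply with both texts. The documents support neither. What remains is that no text states whether exclusion 2a covers an on-study rash, or which rash rule takes precedence.

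On Grade 3/4, a related Grade 4 event, or two of the same Grade 3 event, within 28 days would halt the study (Section 7.6). Withdrawn subjects still have rash follow-up to resolution and an OV4 set. So a reader should not infer that they are lost altogether; the loss is of scheduled visits and samples.

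A reader might also infer that the rule chosen necessarily changes the SAP tables, since SAP Table 6 separates TEAEs leading to study withdrawal from those leading to study drug withdrawal. Neither document says how a subject stopped under Section 7.4.1 is coded, and that section sits under the withdrawal criteria, so the effect depends on coding.

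Finally, persistence wording appears in three of the four places and may be the sponsor's intent.

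**Conclusion.** The protocol is wrong as written, as an internal conflict in its safety rules, on three counts.

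1. **Withdrawal after related Grade 3/4 rash.** This is a direct conflict between Appendix 4 and Section 7.4.1. Withdrawal gives no protection beyond withholding dose 2 and costs up to 8 PK and 5 ADA samples per subject if it follows the Day 7 sample, or 3 of each after Day 30.
2. **Fever limit.** This is a conversion error of about 0.2°C, small in reach but in a criterion that decides dosing.
3. **Re-dosing after transient or responding Grade 2 rash.** The texts differ, with a safe course available: withholding dose 2 satisfies all of them.

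The size is modest. The 44 subjects are an upper bound, not a count of those affected. The documents give no rash rate. Section 4.3 reports blinded review of 66 subjects (6 cohorts × 11) after a first dose of 50 to 450 mg or placebo, with nothing concerning, and how many second doses were still pending is not stated. Few events are expected. The analyses are descriptive, so no test or error rate is at risk.

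**What to change.** - **Appendix 4, Grade 2 and Grade 3/4.** Replace the withdrawal instruction with: *receive no further study drug and complete all remaining scheduled visits of that dosing period, with AE follow-up through the cohort's protocol-defined window (4 months for 1A/1B; Day 206 for 2A, 2B, 3A, 3B and 4B)*. The AE window needs stating because OV4 after dose 2 is Day 168, short of Day 206.
- **Appendix 4, Grade 3 fever criterion.** Change to *>38.0°C (100.4°F)*.
- **Re-dosing after related Grade 2 rash.** State one rule in the synopsis, Section 7.4.1, Appendix 4 and Appendix 5. The safe default is no dose 2. If the sponsor confirms that the persistence condition is intended, amend Appendix 4 to match and make clear when the Appendix 5 rechallenge sentence applies.

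The cost is a few words in four places. No new procedure is needed, because the visits and AE windows already exist.
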